Water Immersion and Polyp Detection: A Randomized Controlled Trial

Edited April 23rd 2019

NCT03231917

Introduction

Although water can be used to facilitate colonoscope insertion¹⁻¹³, the use of two techniques employing water have been evaluated for their effects on adenoma detection as compared to standard insertion methods which employ air or CO₂^{14, 15}. These techniques are called water exchange (WE) and water immersion (WI). In WI, water is used to distend the colon during insertion and is removed largely during withdrawal. WI utilizes enough water during insertion to identify the luminal direction but dirty water is removed primarily during withdrawal. WE is a slower insertion technique in which the air valve is turned off and clean water is infused and dirty water is suctioned during insertion and the instrument is not advanced until the lumen is clean. WE also involves aspiration of retained gas pockets during insertion. Both WE and WI use air or CO₂ rather than water to distend the lumen during withdrawal, and therefore it is not known whether visualization of the mucosa using water as a medium, as opposed to air or CO₂, increases adenoma detection¹⁶. In contrast to the other methods, TUC involves water exchange (WE) during insertion followed by continuous water infusion (rather than gas) on withdrawal in order to distend the lumen for total underwater mucosal visualization.

The use of water during colonoscopy may improve adenoma detection through several possible mechanisms¹⁷. It may help to further clear the bowel of any residual stool. In addition, since water may allow for mucosal inspection without fully distending the lumen like air does, water techniques might increase the yield for flat lesions. Very flat lesions may be less visible with full distention of the lumen. Finally, water has a magnifying effect, which may also increase detection. Thus, TUC, in which the entire procedure including withdrawal is performed underwater, could potentially improve polyp detection compared to gas insufflation.

The goal of our study was to use TUC in tandem with standard CO₂ insufflation to determine if water is a better medium than CO₂ for visualizing and detecting polyps and adenomas. Our goal was to randomize patients to tandem colonoscopy performed first with either TUC or CO₂ followed by the other medium in order to compare miss rates for

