The randomization envelope was opened prior to the initial insertion. An assistant measured the inspection time with a stopwatch from insertion of scope into the rectum until the cecum was reached, stopping the watch during insertion for polyp resection in both techniques or for time spent washing or suctioning (in CO₂ arm only). For the arm where CO₂ insufflation was used first, the lumen was distended with the gas during insertion. When the TUC technique was used first, the air valve was shut off and water was infused and any residual stool or air was suctioned out during insertion. After the cecum was intubated, the endoscopist attempted to intubate the terminal ileum. The mucosal inspection was then initiated during withdrawal when the distention with water or CO₂ was adequate for visualization. Measurement of withdrawal and inspection times was initiated at this point. Inspection time was the withdrawal time minus the time for biopsy or polypectomy or for time spent washing or suctioning (in CO₂ arm only). The assistant with a stopwatch announced the withdrawal time periodically with the goal to equalize inspection times.

When the withdrawal of the colonoscope reached the rectum and after the retroflexion was performed, the endoscopist re-inserted the colonoscope using the other technique. For the exams with TUC as the first method, water was suctioned out of the lumen as CO₂ was introduced into the lumen during the second insertion. Upon withdrawal, the remaining water was aspirated and CO₂ was used to distend the lumen to allow for adequate inspection of the mucosa. In the group in which CO₂ is used first, CO₂ was suctioned out during the second colonoscopy as the scope was inserted with water infusion. As the scope was withdrawn, water was infused with the air valve turned off. Inspection was not started until after cecal intubation and the lumen was filled with water allowing for adequate visualization of the mucosa through the infused water. Inspection time was measured as outlined above.

Outcomes

The primary outcome measure and study endpoint was the miss rate for polyps and adenomas in the two study groups ¹⁸. Miss rates were also calculated for participant level for each technique. Adenoma-level miss rates were calculated as the number of additional adenomas detected during the second examination (for both insertion and withdrawal) divided by the total number of adenomas detected during insertion and

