withdrawal for both examinations. These miss rates were reported for the technique used for the first examination. Participant-level miss rates were calculated as the number of participants with one or more adenomas detected during the second examination, divided by the total number of participants with at least one adenoma in either examination. We also examined proximal (cecum, ascending colon, transverse colon and splenic flexure) adenoma miss rates as a secondary outcome, which were calculated as above. Finally, we also calculated serrated polyp (hyperplastic, sessile serrated polyp and traditional serrated adenoma)

For each polyp, we estimated size by open forceps, and noted location, method of removal, whether polyps were detected by insertion or withdrawal and whether CO₂ or TUC was used for mucosal inspection.

We used the Boston Bowel preparation score to assess the quality of the preparation. We also used a scale of good (3), fair (2) and poor (1) to assess the clarity or turbidity of the water during TUC for 3 segments, right, transverse and left colons.

Co-variates

Data collected included participant age and sex, exam indication, personal history of colorectal neoplasia, family history of CRC, time (total procedure, insertion and inspection), volume of water infused during insertion and withdrawal, quality of bowel preparation as measured by the Boston Bowel Preparation Score and medications provided during the procedure.

Statistical considerations

In calculating a sample size required to detect a clinically important difference in miss rates between TUC and CO₂ we used the following assumptions: a 30% adenoma miss rate for regular colonoscopy^{19, 20}; a 10% adenoma miss rate with TUC; 50% of participants would have at least one adenoma, and participants with adenomas would have an average of two adenomas. We based this in part on a tandem study using cap since the cap had similar reported increase in adenoma detection to water exchange¹⁸. For the study to have 80% power to detect a 3-fold reduction in adenoma miss rates, by using a chi-square test with a 5% significance level, the study needed 60 adenomas per group. We assumed that each participant would have on average two polyps and planned to enroll at least 120 participants (60 at each site).

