Participants who underwent initial colonoscopy with TUC were compared with participants who underwent colonoscopy with CO₂ first for differences in age and propofol dose by using 2-sample t-tests, for differences in sex and indication by using chi square tests, and for a difference in quality of bowel preparation by using a Mantel-Haenszel test for ordered categories. Logistic regression was used to compare the miss rates between participants who underwent TUC first and participants who underwent CO₂ first. The model was adjusted for participant age, sex, family history of CRC, exam indication, time for inspection, insertion time and volume of water infused/aspirated. A generalized estimating equation was used to control for the effect of the endoscopist.

6. Leung FW. Water exchange may be superior to water immersion for colonoscopy. *Clinical gastroenterology and hepatology : the official clinical practice journal of the American Gastroenterological Association* 2011;9:1012-4.

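### The only miss-rate comparison described adjusts for three variables that arise after randomisation and can depend on technique, so it does not estimate the effect that was hypothesised and powered

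*Combined protocol and SAP*

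**What the plan says.** The hypothesis at the end of the Introduction is that TUC has a lower adenoma and polyp miss rate than CO₂. The Outcomes section attributes miss rates to the first technique: "These miss rates were reported for the technique used for the first examination".

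The sample size in Statistical considerations assumes miss rates of 30% and 10%, 60 adenomas per group and 80% power, "by using a chi-square test with a 5% significance level". No covariates enter that calculation.

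The analysis paragraph then describes a different comparison: "Logistic regression was used to compare the miss rates between participants who underwent TUC first" and those who underwent CO₂ first. The model is adjusted for age, sex, family history of CRC and exam indication, and also for "time for inspection, insertion time and volume of water infused/aspirated". A generalized estimating equation handles the endoscopist. The chi-square tests in that paragraph concern sex and indication only.

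The Co-variates section lists "time (total procedure, insertion and inspection), volume of water infused during insertion and withdrawal" without saying which examination is meant. Under Colonoscopy, every participant has both: after the first withdrawal, "the endoscopist re-inserted the colonoscope using the other technique".

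**The concern.** The allocation was opened before the first insertion, so insertion time, inspection time and water volume all come after randomisation. Two of them are tied to the technique by the document's own description.

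- **Water volume.** "TUC involves water exchange (WE) during insertion followed by continuous water infusion (rather than gas) on withdrawal". First-examination volume would be close to a marker of the assigned arm. The Introduction also suggests that water may improve detection by clearing residual stool, so volume may carry part of the effect under test.
- **Insertion time.** "WE is a slower insertion technique in which the air valve is turned off", and TUC uses water exchange for insertion. Adenomas found on insertion count in the miss rate.
- **Inspection time.** This is the weaker case, because the protocol tried to equalise it. However, washing and suctioning time is deducted under CO₂ only, so the variable is not measured in the same way in the two techniques.

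Holding these variables fixed can cost power through collinearity with arm. It can remove a real effect that runs through them, and it can create a spurious effect if an unmeasured factor influences both them and misses. The answer to the hypothesis then depends on a covariate definition that the plan leaves open.

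**Working it through.** **1. Inputs from the documents.** Miss rates 0.30 and 0.10; 5% level (two-sided assumed); 80% power; 60 adenomas per group; half of participants with an adenoma, two each on average; at least 120 participants. The documents give no correlation between arm and the procedural variables, so every such value below is an assumption.

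**2. The plan's own figure.** Enrolment: 120 × 0.5 × 2 = 120 adenomas, or 60 per group. With mean rate 0.20, the chi-square requirement without continuity correction is

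n = [1.96·√(2·0.2·0.8) + 0.84·√(0.21 + 0.09)]² / 0.2² ≈ 62,

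and power at 60 per group is 78.9%. The stated 60 and 80% are reproduced, for an unadjusted contrast of independent adenomas. The planned odds ratio is (0.1/0.9)/(0.3/0.7) = 0.26.

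**3. Collinearity by formula.** If a covariate has correlation r with arm, the variance of the arm coefficient is inflated by VIF = 1/(1 − r²), and power ≈ Φ(2.80/√VIF − 1.96).

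| r | VIF | Power from 80% | Power from 78.9% |
|---|---|---|---|
| 0.5 | 1.33 | 67.9% | 66.7% |
| 0.8 | 2.78 | 39.0% | 38.1% |
| 0.9 | 5.26 | 23.0% | 22.5% |

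**4. Power by simulation.** There were 2,500 trials per scenario with 60 independent adenomas per arm, analysed by ordinary logistic regression with a Wald test. Both models contain age, sex, family history (assumed 20%), indication (assumed three categories) and three endoscopists as fixed effects, a simplification of the planned GEE. They differ only by the three procedural variables. Inspection time is simulated as equalised. An r between arm and covariate corresponds to an arm gap of 2r/√(1 − r²) within-arm SDs. About 1-2% of trials did not converge and were excluded from both models.

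| Assumed link with arm | Power without the three | Power with the three |
|---|---|---|
| None (possible with totals over both examinations) | 77.9% | 77.9% |
| Insertion time r = 0.5 | 79% | 68% |
| Volume r = 0.5 / 0.8 / 0.9 | 77-79% | 67 / 36 / 23% |
| Volume 0.5 and insertion time 0.5 | 77% | 56% |
| Volume 0.8 and insertion time 0.5 | 79% | 35% |

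**5. Effect carried by the covariate.** A simpler simulation (1,500 trials per scenario) used one covariate with an assumed 2 SD gap between arms, so r = 2/√(2² + 4) = 0.71.

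| Share of effect carried | Median odds ratio, unadjusted → adjusted | Power, unadjusted → adjusted |
|---|---|---|
| None | 0.25 → 0.25 | 79% → 48% |
| Half | 0.26 → 0.50 | 80% → 15% |
| All | 0.27 → 0.99 | 77% → 4% |

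**6. No true difference (20% in both arms).** The model is that of step 4, with a latent factor added that raises the log odds of a miss by 0.5 per SD and correlates 0, +0.3 or −0.3 within arm with insertion time and with volume.

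| Scenario | Median odds ratio with the three |
|---|---|
| No shared factor, any r | 0.98-1.00 |
| Shared factor, both variables unrelated to arm | 0.97-1.00 |
| Opposite signs, insertion time r = 0.5, volume r = 0.5 | 1.01-1.02 |
| Opposite signs, insertion time r = 0.5, volume r = 0.8 | 0.78 or 1.18 |
| Same sign, insertion time r = 0.5, volume r = 0 | 0.84 or 1.21 |
| Same sign, insertion time r = 0.5, volume r = 0.5 | 0.71 or 1.42 |
| Same sign, insertion time r = 0.5, volume r = 0.8 | 0.58 or 1.77 |

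The false-positive rate is about 6% in the cases without bias, 6-7% with opposite signs at volume r = 0.8, and 7-11% in the same-sign cases. Without the three variables, the odds ratio is 0.98-1.03 and the false-positive rate 4-6%.

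Clustering of adenomas within participants is ignored throughout, as in the plan's chi-square calculation; it is a separate issue.

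**The case against.** The strongest reply is that the damaging reading may not be the intended one. In the TUC-first group the remaining water is aspirated during the second examination, so a complete infused/aspirated volume spans both. The Co-variates section likewise mentions total procedure time and does not split volume by examination. Totals could be nearly unrelated to arm, and the harm could then be negligible. This stands as a limit on the size. It does not settle the matter: the plan does not say that totals were used, and totals are still post-randomisation and include the examination in which misses are counted.

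Second, the Introduction also frames the goal as whether water or CO₂ gives the better view of the mucosa. For that narrower question, holding time constant is arguable, most clearly for inspection time. It does not justify adjusting for water volume, and the plan names no direct effect as its target.

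Third, sizing a trial on a simple test and analysing it with an adjusted model is not in itself an error, the logistic model is never labelled primary, and crude miss rates are reported by first technique. All true. But baseline adjustment still compares the groups as randomised, whereas adjustment for consequences of technique does not. Reporting crude rates also does not designate a test, and the analysis paragraph does not carry the powered chi-square forward.

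Finally, the bias figures need an assumed latent factor; without one, the null odds ratio stays at 0.98-1.00. That is correct, and the figures show what can happen, not what did.

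**Conclusion.** The concern holds. The only between-group miss-rate model described conditions on three variables that follow randomisation. Two of them, water volume and insertion time, are linked to technique by the document's own account; inspection time is a minor case. The resulting odds ratio matches neither the hypothesis nor the contrast that was powered. That mismatch follows from the text and needs no assumption.

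The size does rest on assumptions. It runs from no loss, if the values are totals unrelated to arm, to power of 23% with first-examination volume at r = 0.9. If the covariate carries the effect, a true difference can be largely or wholly adjusted away. Bias under no true difference requires an unmeasured shared factor and can go in either direction. The sample-size figure is sound for the chi-square; it does not describe the power of the model that was specified.

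**What to change.** - Remove insertion time and water volume, and for consistency inspection time, from the primary miss-rate model.
- Define the primary comparison by technique used first, either unadjusted or adjusted only for age, sex, family history of CRC and exam indication. State in advance which of the two it is, and account for endoscopist/site as the stratification factor. Either keeps about the planned power: 79-82% for the chi-square and 77-79% for the baseline-adjusted model in simulation.
- Report insertion time, inspection time and water volume descriptively, by arm and by examination.
- Keep the model containing them as exploratory, stating which examination each value comes from.

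The cost is SAP wording and a re-run, with no new data. The time- and volume-adjusted estimate would no longer be available as the main answer. The document is written in the past tense, so if analysis has begun the change must be disclosed as post hoc, with both models shown.

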polyps and adenomas. Our hypothesis was that TUC was associated with a lower adenoma and polyp miss rate for tandem performance of colonoscopy than CO₂.

Methods

We conducted a randomized trial of tandem colonoscopies comparing TUC to CO₂ insufflation. Our study was approved by the Institutional Review Boards at the White River Junction Veterans Affairs Medical Center and Indiana University. All patients were consented with written consent prior to the colonoscopies. In one group, TUC was employed as the first method for mucosal inspection while in a second group, CO₂ insufflation was used first.

Study Population

Eligible subjects were adults 50-80 years who presented for colonoscopy at White River Junction VAMC, Indianapolis VAMC, and Indiana University. Exclusion criteria included a co-morbid status of American Society of Anesthesiologists physical status classification system ASA of III (severe systemic disease) or higher, Inflammatory Bowel Disease (IBD), surgical resection of the large bowel, as well as the use of non-aspirin anticoagulants. Finally, potential subjects who did not report a clear effluent in the most recent bowel movement at time of colonoscopy were excluded from the study.

Randomization

The participants were randomized using a random number generator, stratified by endoscopist/site. The results of the randomization were opened prior to the initial insertion of the colonoscope, informing the endoscopist which method was first, CO₂ or TUC.

Colonoscopy

Consenting adults were randomized to undergo colonoscopy with either TUC or CO₂ insufflation for the first colonoscopy followed by an examination using the other technique. All examinations were performed by one of three experienced endoscopists ([name], [name], [name]). Participants were sedated using propofol or moderate sedation with midazolam/fentanyl and diphenhydramine. All colonoscopies were performed with high definition colonoscopes. (Olympus CF-HQ190L; Olympus (Tokyo, Japan))

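### The GEE for endoscopist in the primary miss-rate comparison is unspecified, and its usual robust-error form is unreliable with only three endoscopists

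*Combined protocol and SAP*

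**What the plan says.** The Outcomes section sets the endpoint: "The primary outcome measure and study endpoint was the miss rate for polyps and adenomas in the two study groups". The adenoma-level rate counts lesions; a separate participant-level rate counts people.

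Statistical considerations compares these rates between the TUC-first and CO₂-first groups by logistic regression. The model adjusts for age, sex, family history, indication, inspection time, insertion time and water volume. On dependence it says only: "A generalized estimating equation was used to control for the effect of the endoscopist". It does not state the unit of the regression, the cluster, the working correlation, the variance estimator, any small-sample correction or the reference distribution. Nothing is said about several lesions in one participant.

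The Colonoscopy section says: "All examinations were performed by one of three experienced endoscopists". The Randomization section says: "The participants were randomized using a random number generator, stratified by endoscopist/site". The sample size is worked out "by using a chi-square test with a 5% significance level". It assumes that "participants with adenomas would have an average of two adenomas", and for polyps: "We assumed that each participant would have on average two polyps".

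**The concern.** A GEE said to control for the endoscopist would ordinarily be run with endoscopist as the cluster and sandwich standard errors. The sandwich variance is estimated from the spread between cluster totals, and here there are three. Its large-sample justification needs many clusters.

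The logistic model is the only stated comparison of the primary miss rates. The choice of test therefore decides whether the trial produces false positives at several times the nominal rate, has little power, or cannot reject at all. The plan does not name the test, so even the direction of the error is open.

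**Working it through.** **Inputs from the documents.** Three endoscopists (Colonoscopy). From Statistical considerations: miss rates 30% and 10%, half of participants with an adenoma, two adenomas in each of these, two polyps per participant, at least 120 participants, 5% level, 80% power, 60 adenomas per group.

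**Assumptions, not in the documents.** Within-participant ICC 0 to 0.3. A 20% miss rate in both arms under the null. The same miss rates for polyps. Endoscopist loads of equal thirds or 2:1:1. Equal arms within endoscopist. Two-sided tests.

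**1. The plan's own figure.** n = [1.96·√(2·0.2·0.8) + 0.842·√(0.3·0.7 + 0.1·0.9)]² / 0.2² = (1.109 + 0.461)² / 0.04 ≈ 62 per group. With 60 per group, power is 78.9%. The stated 60 reproduces closely if lesions are independent. The expected yield agrees: 120 × 0.5 × 2 = 120 adenomas, 60 per group.

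**2. Wald test with three equal clusters.** Treat the arm effect as the mean of three roughly normal cluster effects d₁, d₂, d₃. The sandwich variance is Σ(d−d̄)²/9, whereas a t statistic uses Σ(d−d̄)²/6. So z = t₂·√1.5, and P(|t₂| > x) = 1 − x/√(2 + x²).
- Reference 1.96: x = 1.96/1.2247 = 1.600, giving 25.1% null rejection.
- Reference t on 2 df (4.303): x = 4.303/1.2247 = 3.513, giving 7.2%.

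Neither result involves within-participant correlation.

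**3. Generalized score test.** With cluster contributions U₁, U₂, U₃ the statistic is (ΣU)²/ΣU², which is at most 3 (Cauchy–Schwarz). The 5% critical value is 3.84. P(χ²₁ > 3) = 0.083, so the test can never reject.

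**4. Simulation without covariates.** 4,000 null and 3,000 alternative trials per cell; 60 adenoma-bearing participants (zero-truncated Poisson, mean 2) or 120 participants with polyps (Poisson, mean 2); beta-binomial misses; independence working correlation. Ranges cover both loads and ICC 0 to 0.3; arrows run from ICC 0 to ICC 0.3.

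| Method | Null, adenomas | Null, polyps | Adenoma power |
|---|---|---|---|
| Endoscopist cluster, sandwich, z | 24–26% | 24–27% | not quoted |
| Same, t on 2 df | 6.6–7.6% | 6.8–8.3% | 30–41% |
| Same, generalized score | 0 | 0 | 0 |
| Model-based errors | 4.7–4.9% → 9.0–9.3% | 4.8–5.3% → 11.4–11.9% | not quoted |
| Chi-square | 5.2–5.5% → 10.0–10.2% | 5.0–5.5% → 11.7–12.3% | 80% → 76% |
| Participant cluster, endoscopist fixed, Kauermann-Carroll, t | 3.9–5.4% | 4.4–5.6% | 75% → 58% |

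The Monte Carlo standard error is about 0.35 points at 5% and 0.9 points for power. Separately coded runs gave 23–27% for the endoscopist-clustered z test, and 33–42% power for t on 2 df.

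**5. The adjusted model.** Seven adjustment terms, arm and intercept make at least nine parameters. The fitted score contributions of three clusters sum to zero, so the sandwich covariance has rank at most 3 − 1 = 2; a nine-parameter fit confirmed rank 2. Indicative runs (adenomas, 2:1:1 load, seven null covariates, one correlated 0, 0.5 or 0.8 with arm) gave null rejection of 29–31% for the endoscopist-clustered z test, 8.3–10.1% for an uncorrected participant-clustered z test, and 4.2–5.0% with Kauermann-Carroll.

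**6. The other reading, by hand.** If lesions are treated as independent, the variance is understated by 1 + (m* − 1)·ICC, where m* = E(m²)/E(m).
- Polyps: Poisson mean 2 gives m* = 3. At ICC 0.3 the factor is 1.6, and P(|Z| > 1.96/√1.6) = 12.1%.
- Adenomas: zero-truncated Poisson with mean 2 has λ ≈ 1.594, so m* = 2.594. The factor is 1.478, and the rejection rate is 10.7%.

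Both are close to the simulated chi-square figures.

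**The case against.** **The estimator is not stated.** This is the strongest objection, and it stands in part. A reader might infer that the trial's primary test has a false-positive rate of about 25%. The documents do not support that as a fact. It follows only if endoscopist is the cluster, the errors are sandwich errors and the reference is normal. Under model-based errors, or with endoscopist as an adjustment factor with model-based errors, there is no three-cluster problem.

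**Within-participant correlation.** A reader might infer that these alternatives are shown to be invalid too. They are not. They are about nominal at ICC 0, and the 9–12% needs an assumed ICC of 0.3.

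**Covariates.** The main figures come from a model without covariates, and the adjusted runs are only indicative. That stands for the exact sizes. The adjusted runs point the same way, and the score bound and the rank limit do not depend on the covariates.

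**Endoscopist clusters contain the participants.** In principle, then, the sandwich covers correlation within participants. But three clusters cannot estimate that variance reliably.

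**The chi-square test might be the primary analysis.** The plan uses it only for the sample size; the logistic model is the stated comparison.

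**Stratified randomization already deals with endoscopist.** It balances the arms within endoscopist. That argues for the stratum as a fixed factor, not for three robust clusters.

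**Conclusion.** The plan needs correcting here. What is certain is that the only provision for dependence is a GEE for endoscopist, that there are three endoscopists, and that no cluster, variance estimator or reference distribution is given. On the natural reading the primary test fails whichever usual reference is used: about a quarter of null trials rejected with Wald z (29–31% in the indicative adjusted runs), roughly 30–42% adenoma power with t on 2 df, or no possible rejection with the score test. This holds at ICC 0, so it does not rest on the assumed correlation. It does rest on that reading of one sentence, which is why confidence in the size is moderate.

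It would be wrong to infer that the 60-per-group arithmetic is faulty. It reproduces on its own independence assumption; the weakness is in the analysis method.

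**What to change.** State the unit, cluster, variance estimator and reference distribution of each regression, and do not use robust errors on three endoscopist clusters.

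- **Adenoma- and polyp-level rates:** logistic GEE with participant as the cluster and endoscopist/site, the randomization stratum, as a fixed factor. Use a small-sample-corrected robust variance, for example Kauermann-Carroll, with a t reference and stated degrees of freedom. One choice is participants contributing lesions minus model parameters. With 60 adenoma-bearing participants, seven single-term covariates and three strata, that is 60 − (1 + 1 + 2 + 7) = 49.
- **The correction is required.** Without covariates the uncorrected participant-clustered z test is only slightly liberal (5.5–6.7% for adenomas), but in the adjusted model it can reject about 8–10% of null trials.
- **Alternative:** a participant random intercept, noting that it estimates a conditional rather than a marginal odds ratio. Without covariates, its likelihood-ratio test rejected 4.3–5.7% of null adenoma trials.
- **Participant-level rates:** ordinary logistic regression with endoscopist/site as a fixed factor (null rejection 4.3–5.6% without covariates).

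Which covariates to keep is a separate question.

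**Cost.** A short SAP paragraph, a changed cluster identifier and a variance option. The text is in the past tense, so this may mean a re-run on data already held; no new data are needed. The strata take at least two degrees of freedom, and more if an endoscopist worked at several sites: the Study Population section names three places, while 60 per site out of 120 implies two. Adenoma power without other covariates is about 75%, 70%, 64% and 58% at ICC 0, 0.1, 0.2 and 0.3, against the stated 80%; polyp power is 86–97%. Part of the chi-square test's higher power above ICC 0 comes from excess false positives. The power should be restated, not met by enrolling more participants.
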